**Developing a Tool to Support Shared Decision-Making Post-Concussion  
Between Adolescents, Parents and Clinicians**

**NCT Number:** NCT04777864

**Document Date:** 03/17/2022

*Due to the smaller sample recruited we simplified our analytic plan to focus on between-condition comparisons for the primary decision-related outcomes and no subgroup comparisons.*

## 1. Objectives

### 1.1. Purpose, specific aims, or objectives:

The purpose of this study is to understand the perspectives of adolescents, parents, and clinicians on the decision to resume or cease sport participation following recovery from a sport-related concussion. Specifically, this study will test the effectiveness of created decision aids to help with this understanding and discussion. The specific aims of this study are four-fold:

**Aim 1:** Conduct surveys with clinicians (inclusive of pediatrician and family medicine providers) and families who have an adolescent recovering from a sport-related concussion (one parent and one adolescent) about their experiences discussing return to sport. Specifically, this aim will survey clinicians about their current knowledge and belief of concussion research, their experiences with discussing return to sport post-concussion with families, and their opinions for best practices and needs for creating an effective shared decision-making aid with families on this topic. This aim will also survey parent-adolescent dyads about their experiences making the decision to return to sport. Findings from this aim will directly influence Aims 3 and 4.

**Aim 2:** First, this aim will include semi-structured interviews (inclusive of cognitive interviewing, qualitative interviewing) with families (one parent and one adolescent) in order to learn more about their experiences making decisions to resume or stop sport participation after recovery from a sport-related concussion. Second, this aim will conduct usability testing with families (one parent and one adolescent) and their clinicians with created parent and adolescent decision aids for enabling return to sport discussions following a sport-related concussion. Specifically, this aim will involve usability tests (i.e., interview + tasks) to evaluate the effectiveness of current decision aids for parent and adolescent and provide feedback on ways to tailor the current decision aids better. Findings from this aim will be used directly in Aim 4.

**Aim 3:** First, this aim will include semi-structured interviews (inclusive of cognitive interviewing, qualitative interviewing) in order to receive directed and specific clinician feedback on how to create a decision aid effectively for their use.

**Aim 3 (continued):** Second, this aim will conduct usability testing with clinicians (including pediatricians and family medicine providers) for a clinician-specific decision aid. The findings from Aim 1 and Aim 2 will help inform the creation of a clinician-specific decision aid. Findings from this aim will be used directly in Aim 4.

**Aim 4:** This aim has two cohorts:

Aim 4a: Cohort 1 will evaluate how shared decision making currently occurs in a clinical appointment. This data will then be used to compare need and impact of the intervention group in Aim 4b.

Aim 4b: Cohort 2 includes a pilot random control trial (RCT) of all three decision aids (i.e., parent, adolescent, clinician) to assess intervention efficacy of all decision aids in aiding family shared decision making in returning to sport post-sport related concussion.

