**3. Study Endpoints**

**3.1. Primary and secondary endpoints:**

**Aim 1:** Recruitment of participants will occur until thematic saturation, or until 500 participants are reached (100 clinicians, 200 parents, 200 adolescents). For each participant, the endpoint will be the conclusion of the survey.

**Aim 2:** Recruitment of participants will occur until thematic saturation. For each participant, the endpoint will be the conclusion of the interview and/or usability testing.

**Aim 3:** Recruitment of participants will occur until thematic saturation. For each participant, the endpoint will be the conclusion of the usability testing.

**Aim 4a and 4b:** Recruitment will continue until 40 families agree to participate (20 per phase) and up to 20 healthcare providers (Aim 4b only). For each family, participation will conclude after completing the 3-month follow-up survey. For each healthcare provider, participation will conclude after completing the brief survey about tool implementation.

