**3.2. Primary or secondary safety endpoints:**

There are no primary or secondary safety endpoints for this study.

**4. Drugs, Devices and Biologics****4.1.** Manufacturer and name of all drugs, devices and biologics:

N/A

**4.2.** Description and purpose of all drugs, devices and biologics:

N/A

**4.3.** Regulatory status of all drugs, devices and biologics:

N/A

**4.3.1.** Drugs or Biologics:

IND Exempt. Explain: [Click here to enter text.](#)  
 IND.

**4.3.2.** Devices:

IDE Exempt. Explain: [Click here to enter text.](#)  
 Abbreviated IDE / Non-Significant Risk. Explain: [Click here to enter text.](#)  
 IDE / Significant Risk.

**4.4.** Plans to store, handle, and administer any study drugs, devices and biologics so they will be used only on subjects and be used only by authorized investigators:

N/A

**5. Procedures Involved****5.1.** Study design:

This study involves the following procedures:

**Aim 1:** Survey**Aim 2:** Interviewing (i.e. qualitative) and Usability Testing**Aim 3:** Interviewing (i.e., cognitive, qualitative) and Usability Testing**Aim 4a and 4b:** Consecutive cohort design (families). Healthcare providers will also complete a one-time survey.**5.2.** Research procedures:

**Aim 1: Clinicians:** This aim will survey clinicians about their current knowledge and belief of concussion research, their experiences with discussing return to sport post-concussion with families, and their opinions for best practices and needs for an effective shared decision-making aid with families on this topic. Participants will receive a link to an online survey, hosted on a survey-hosted site (e.g., REDCap). Before beginning the survey, participants will read an information sheet about the study and then proceed to the survey, which will ask them questions relating to the topics described above. After completing the survey, participants will be exited from the survey and data collection will end for this aim. Survey questions can be found in the attachment section on Click.

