**Aim 3:** This aim involves semi-structured interviews, and usability testing with clinicians as described below. Usability testing will be informed by the interviews and will be submitted for IRB review after the interviews are complete. Participants (i.e., clinicians) will participate in a 60-minute interview, either in person or online. Prior to the start of the interview, participants will review an information sheet about the study that will either be emailed to them (if session is conducted online) or printed and handed in person (if session is conducted in person). Then, they will be interviewed (inclusive of cognitive interviewing, qualitative interviewing,) about specific clinician feedback on how to create a decision aid effectively for their use. All interview data will be audio recorded. All documents used in this aim can be found in the attachment section of Click. All interviews conducted online will be done so through an online platform (i.e., Zoom) and their online session will be recorded.

**Aim 4a and b:** In the first data collection cohort (Aim 4a), there will be no change to the nature of provider communication with families seeking care for their child's concussion. In the second cohort (Aim 4b), the study team will share the respective decision aids with the family and let them know to complete them before their appointment. After both the parent and adolescent complete their respective decision aids, a member of the study team will insert the clinician tool link in the patient's chart and/or send a message with the link for the clinician to review, prior to the appointment.

Data will be collected about the experience that families have discussing the decision of what sports and activities they participate in after they recover from their injury and using their respective decision aids (intervention only). Survey data will be collected from parents and adolescents at several time points (baseline, post-visit(s) up to and including their final visit, 3-months after initial visit). Survey data will also be collected from healthcare providers about their experiences sharing information with families and using the tool (intervention only) over this time period. Data will be collected at one time point (after a patient of the healthcare provider has completed the tool).

**5.3.** Data sources that will be used to collect data about subjects:

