**Aims 4a and 4b:** Survey data will be collected from up to 40 families (parent + child) (20 per phase) at a minimum of 3 time points: their first visit, after each following visit up to and including their final visit, and 3-month follow-up (i.e., 3 months after their initial visit). Data will come from online surveys, completed online or in-person while at their visit (e.g., participants will be given a tablet to complete while waiting). If participants are not able to complete the relevant surveys in-person at their visit, they will complete the follow up survey by telephone (call or text linking to a survey hosted on REDCap), or by email (linking to a survey hosted on REDCap). Survey data will also be collected from up to 20 healthcare providers at one time point (towards the end of family data collection) about their experiences using the tool.

For participants enrolled in the intervention group (4b only), online data will also be collected within their respective decision aids. See the online versions of "Parent Tool", "Adolescent Tool", and "Family Discussion Tool" attached to the Click SmartForm, to see the data that will be collected within the decision aids.

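### Section 1.1 calls Aim 4b a pilot randomised trial, but sections 5.1, 5.2 and 5.4 describe a non-randomised comparison of two consecutive cohorts

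*Combined protocol and SAP*

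**What the plan says.** The objectives and the procedures give different accounts of how families come to be treated or untreated in Aim 4.

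- Section 1.1, Aim 4b: "Cohort 2 includes a pilot random control trial (RCT) of all three decision aids", with the stated purpose of assessing efficacy.
- Section 1.1, Aim 4a, on the Cohort 1 data: "This data will then be used to compare need and impact of the intervention group in Aim 4b". The comparator is therefore Cohort 1.
- Section 5.1, for Aims 4a and 4b: "Consecutive cohort design (families").
- Section 5.2, first cohort: "there will be no change to the nature of provider communication with families".
- Section 5.2, second cohort: "In the second cohort (Aim 4b), the study team will share the respective decision aids with the family".
- Section 5.4, on data captured inside the aids: "For participants enrolled in the intervention group (4b only").
- Section 3.1: "Recruitment will continue until 40 families agree to participate (20 per phase"). Sections 10.1 and 10.4 count families in the same way.
- Section 19.1 gives the two cohorts different start triggers. Aim 4a recruits from the start of the study, and Aim 4b once the aids have been developed from Aims 2 and 3.

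Section 14.1 compares treatment with control and does not say how families were allocated. The cover note reports a smaller sample than planned and says "we simplified our analytic plan to focus on between-condition comparisons for the primary decision-related outcomes".

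**The concern.** Randomisation is the property that lets a difference between groups be read as an effect of the intervention, apart from chance. Section 1.1 claims that property for Aim 4b, and the design sections describe a comparison without it.

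The label matters because of what rests on it. After the simplification described on the cover note, the comparison between conditions on the primary decision outcomes is the main quantitative result. A reader who relies on 1.1 would take it as randomised evidence. Under the design in section 5, a difference could come from the aids, from a change over the enrolment period, or from a different mix of families in the two cohorts. A real benefit could equally be hidden by such a change. Section 14.1 plans to compare baseline characteristics between the groups. It states no adjustment for them or for time, and it does not say that the comparison is non-randomised.

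**Working it through.** No calculation decides this point. The check is whether any reading of the plan reconciles the label in 1.1 with the described conduct.

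1. **Randomisation within Cohort 2.** The verb in 1.1 could suggest a trial nested inside Aim 4b. Section 5.2 gives the aids to the second cohort with no exception, section 5.4 makes Aim 4b the intervention group, and section 1.1 itself takes the comparison data from Cohort 1. Section 10.4 does not fit either. It plans 20 families per phase, expects 20 × 0.85 = 17 to complete (the plan's own figure, which reproduces), and bases power on 15 per phase. Two arms of 15 inside Aim 4b would need 2 × 15 = 30 families, and that phase has 20. The power statement is about phases, not arms within one phase. (The detectable differences in 10.4 are a separate matter and are not used here.)

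2. **Randomisation between Aims 4a and 4b.** This needs a period in which both cohorts are open and families are allocated between them. Section 19.1 sets separate start triggers and describes no allocation step. Section 8.2 gives planned enrolment of 3 months each for Aims 1 and 3 and 6 months for Aim 4a. Section 19.1 starts Aim 3 after Aim 1 is complete. If Aims 1 and 3 run in sequence and finish before 4b opens, 4b opens no earlier than about 3 + 3 = 6 months in, when the planned enrolment to 4a ends. Section 8.2 also allows 4a up to 12 months, so some overlap is possible. Overlap alone would not amount to random allocation.

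3. **Search for an allocation procedure.** The available text contains no sequence, ratio, concealment or control families within 4b. The sentence in 1.1 is the only mention of randomisation. Some front-matter pages between the cover note and the contents list were not available and could not be checked.

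4. **Weight of each section.** Sections 5.1, 5.2 and 5.4 contradict 1.1 directly. The start triggers in 19.1 are consistent with them. Sections 3.1, 10.1 and 10.4 are consistent but weaker, since they count families per phase without saying which condition each phase receives.

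The only reading that fits sections 5 and 19 is a comparison of two consecutive, non-randomised cohorts.

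**The case against.** The strongest reply is that one phrase in the objectives is wrong and nothing else follows. The sections that govern conduct agree with each other, nobody following sections 5, 14 and 19 would randomise or run a different analysis, and no section says that results will be reported as randomised. Section 1.2 describes the research as qualitative with no hypotheses to test, and the study is a pilot. The two cohorts also share a clinic, a recruitment process (19.1) and family eligibility criteria (9.1), and their baseline characteristics will be compared.

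Much of this stands. Conduct would not change, and the shared setting reduces confounding. It does not make allocation random, however, and 14.1 is silent on the point, so the only statement about allocation in the objectives is the wrong one. Section 1.2 does not help, because 10.4 and 14.1 plan a quantitative comparison with a power statement. Pilot status lowers the stakes of the result but not the need to describe allocation correctly.

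Several stronger readings are tempting, and the documents do not support them:

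- **Complete separation in calendar time.** A reader might infer that 4a closes before 4b opens. The plan gives start triggers and durations only, so the degree of overlap is unknown.
- **A specific inflation of the false-positive rate.** Any such figure needs an assumed shift between cohorts. The documents give no estimate of one, and the cover note names neither the achieved sample size nor the simplified test.
- **Removal of the efficacy aim.** A non-randomised pilot may state such an aim if its limits are stated.

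**Conclusion.** The contradiction is real and should be corrected. Section 1.1 gives Aim 4b a property that the design in 5.1, 5.2 and 5.4 does not have. In size, it covers the whole comparison: condition follows cohort for all 40 planned families, 20 in each, and none is described as randomised.

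The result can be reported as a difference between two cohorts. It cannot be reported as randomised evidence. It is open to confounding by enrolment period and case mix, in an unknown direction and amount. Sections 22.2.1 and 22.2.3 mention pandemic restrictions, which is a reason to think that the enrolment period could matter but not a measure of how much.

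A reader might infer that choosing consecutive cohorts was itself an error, or that randomisation should now be added. The documents do not support that. A consecutive-cohort pilot is a legitimate design, and the fault is in its description. The conclusion assumes that sections 5.1, 5.2 and 5.4 describe what was intended and that the unavailable pages contain no allocation procedure.

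**What to change.** 1. In section 1.1, replace the randomised-trial label for Aim 4b with: *the intervention cohort of a non-randomised consecutive-cohort pilot, compared with Cohort 1 (Aim 4a)*. The efficacy wording may stay if the limit in item 2 is stated.
2. In section 14.1, add: *Differences between conditions are non-randomised comparisons, subject to confounding by enrolment period and case mix; enrolment dates will be reported for each cohort.*
3. If families were in fact randomised, leave the label and correct 5.1, 5.2, 5.4 and 19.1 to say how, including where the control families came from.

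Items 1 and 2 take one replaced phrase, one added sentence and a line of dates in the report. No procedure, visit or sample size changes, and the correction can be made after recruitment. The downside is that the permitted conclusion becomes weaker.

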### 1.2. Hypotheses to be tested:

This research is qualitative; therefore, we do not have any hypotheses to explicitly test.

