## 8. Study Timelines

### 8.1. Duration of an individual subject's participation in the study:

**Aim 1:** For each participant, the end point will be the conclusion of the survey.

**Aim 2:** For each participant, the end point will be the conclusion of the semi-structured interview and/or usability session (including interviewing).

**Aim 3:** For each participant, the end point will be the conclusion of the interview.

**Aim 4a and Aim 4b:** For each parent-adolescent dyad participant, the end point will be the conclusion of the 3-month follow-up survey. For healthcare providers (Aim 4b), the end point will be the conclusion of the survey.

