### 10.4. Power analysis:

**Aim 1:** This data is primarily being assessed for qualitative responses; therefore, no power analyses are being assessed.

**Aims 2 & 3:** This data is primarily qualitative, and thus a power calculation is not appropriate.

**Aim 4a and b:** We anticipate enrolling 20 families per study phase; allowing for 15% attrition an estimated 17 per phase would complete the study. Conservatively estimating 15 families per phase, we will have  $\geq 80\%$  power to detect a difference in decisional regret (range: 0 to 100 points) as small as 7.1, 3.0 and 1.2 points, for SD = 12, 5, and 2, respectively. These estimates assume an alpha of 0.05 and SD ranging from 1-12. The data from the healthcare provider survey is primarily qualitative, and thus a power calculation is not appropriate.

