**27. International Center for Harmonization of Good Clinical Practice (ICH-GCP)**

**27.1.** If you have committed to conducting the described study per ICH-GCP, check this box: 

- This is generally applicable for contracts with industry-sponsored studies or sponsor protocols. See your contract/agreement or Sponsor Documentation if you are unsure.
- Note that completing GCP training is a separate activity and does not automatically mean that you have committed to conducting the study per ICH-GCP.
- **If you check the box, upload a current curriculum vitae (CV) for the PI to the “Other Attachments” section of the “Local Site Documents” SmartForm.**

---

 Include information if this protocol is associated with other IRB-approved studies (e.g. is this application the next part/phase of a previously approved application.

 In clinical trials, an endpoint is an event or outcome that can be measured objectively to determine whether the intervention being studied is beneficial. Some examples of endpoints are survival, improvements in quality of life, relief of symptoms, and disappearance of the tumor.

 Include information on a drug or biologic in this section if: (1) the study specifies the use of an approved drug or biologic; (2) the study uses an unapproved drug or biologic; (3) the study uses a food or dietary supplement to diagnose, cure, treat, or mitigate a disease or condition; or (4) data regarding subjects will be submitted to or held for inspection by the Food and Drug Administration (FDA). Only include information on a device in this section if: (1) the study evaluates the safety or effectiveness of a device; (2) the study uses a humanitarian use device (HUD) for research purposes; or (3) data regarding subjects will be submitted to or held for inspection by the FDA. Please note that mobile medical applications may meet the definition of a device – see [FDA Guidance](#).

 See the Investigator Manual HRP-103 for sponsor requirements for FDA-regulated research.

 Explain what IND exemption category applies to the drug and why. Note that a drug is not exempt from an IND unless all criteria for one category are met. See “HRP-306: Drugs” for more information.

 Explain what IDE exemption category applies to the device and why. Note that a device is not exempt from an IDE unless all criteria for one category are met. See “HRP-307: Devices” for more information.

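### Do the no-hypotheses statement in 1.2 and the completion-based endpoints in 3.1 undo the Aim 4 efficacy comparison?

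*Combined protocol and SAP*

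**What the plan says.** Section 1.2 makes a single statement for the whole protocol: "This research is qualitative; therefore, we do not have any hypotheses to explicitly test". It makes no exception for Aim 4.

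Section 3.1 reads as a list of completion events. For Aim 1, "For each participant, the endpoint will be the conclusion of the survey". For Aim 4 it gives 20 families per phase, up to 20 providers, and "For each family, participation will conclude after completing the 3-month follow-up survey". Section 8.1 repeats that content: "For each parent-adolescent dyad participant, the end point will be the conclusion of the 3-month follow-up survey". Footnote 2, attached to the Section 3 heading, explains that in clinical trials "an endpoint is an event or outcome that can be measured objectively to determine whether the intervention being studied is beneficial".

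Other sections describe a comparison:

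- Section 1.1 says that "this study will test the effectiveness of created decision aids" and describes Aim 4b as "a pilot random control trial (RCT) of all three decision aids (i.e., parent, adolescent, clinician) to assess intervention efficacy of all decision aids", with the Aim 4a cohort as comparator.
- Section 10.4 claims at least 80% "power to detect a difference in decisional regret (range: 0 to 100 points") at alpha 0.05. It calls the data primarily qualitative only for Aims 1 to 3 and the provider survey.
- Section 14.1 compares the primary decision process and quality outcomes between conditions by structural equation modelling, with parent and child measures in parallel.
- The front-page note keeps that comparison and drops subgroup comparisons.

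**The concern.** Read literally, 1.2 denies that anything is tested, while 10.4 states an alpha and a power. Section 3.1 adds to the difficulty, because the event it gives for Aim 4 is reached by every family that completes follow-up in either cohort and so cannot show benefit in the sense of footnote 2.

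The primary outcomes are also thinly specified in the text. Decisional regret is named only in 10.4. Section 14.1 speaks of several primary outcomes without listing them, does not rank parent against adolescent, and attaches a time point (Time 3) only to the secondary outcomes. If the document were truly undecided about whether Aim 4 gives an efficacy result, a reader could not tell how to take a finding in one reporter and not the other, and the choice could be made after seeing the data.

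**Working it through.** **1. Which text governs the analysis.** Set side by side, the sections differ in role.

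| Section | What it does for Aim 4 |
|---|---|
| 1.2 | General statement; no analysis instruction |
| 3.1 | Recruitment target and end of participation; no outcome |
| 8.1 | Same completion event as 3.1 |
| 10.4 | Powered difference in decisional regret |
| 14.1 | Model, conditions compared, reporters, secondary outcomes |
| Front-page note | Keeps the between-condition comparison |

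Only 14.1 and the front-page note instruct the analyst, and they agree. Section 1.2 fits the interview and usability work of Aims 2 and 3, and loosely Aim 1, which 10.4 calls primarily qualitative although 14.1 also gives its survey a quantitative analysis. Section 3.1 is silent on outcomes. It does not say that Aim 4 yields no efficacy result.

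**2. The plan's own figures.** Attrition reproduces: 20 × 0.85 = 17 families per phase. The detectable differences in 10.4 (7.1, 3.0 and 1.2 points at SD 12, 5 and 2) correspond to 7.1/12 = 0.59 and 3.0/5 = 1.2/2 = 0.60 SD. With 15 per phase and a two-sided two-sample t-test at 0.05, the power at those differences is 34.7%, 35.5% and 35.5%. The differences detectable with 80% power are 12.72, 5.30 and 2.12 points (1.06 SD). So the power statement does not reproduce. That is a separate matter; here 10.4 serves only to show that a test is intended.

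**3. Would parent and adolescent results conflict?** Inputs: 15 families per phase and alpha 0.05 (10.4); a true effect of 1.06 SD in both reporters, which gives each 80% power; parent-adolescent correlation from 0 to 0.7 (assumed; the documents give none). With independent reporters, the chance that exactly one is significant is 2 × 0.80 × 0.20 = 0.32. With no effect it is 2 × 0.05 × 0.95 = 0.095. Simulation with 200,000 runs gives:

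| Correlation | Exactly one significant, 1.06 SD in both | Exactly one significant, no effect |
|---|---|---|
| 0 | 0.321 | 0.096 |
| 0.3 | 0.272 | 0.090 |
| 0.5 | 0.228 | 0.081 |
| 0.7 | 0.180 | 0.068 |

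Both reporters are given the same true effect, so a split is only one p-value falling on each side of 0.05. The size of real disagreement follows from the sign of the estimates. Each estimate lies 1.06 × √(15/2) = 2.90 standard errors above zero, so it is negative with probability about 0.00185. At correlation 0, opposite signs occur in 2 × 0.00185 × 0.99815 = 0.0037 of studies, and in about 0.003 at correlation 0.7.

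**4. False positives.** Calling either reporter alone a success would give 1 − 0.95² = 0.0975 at correlation 0 and about 0.083 at 0.7. The plan states no such rule.

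**5. Precision available.** The 95% half-width is 2.048 × SD × √(2/15), which gives 8.98, 3.74 and 1.50 points at SD 12, 5 and 2. These follow from the sample size whichever wording is used in 1.2 and 3.1.

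**The case for a change.** The strongest opposing case is textual. Section 1.2 is unqualified, and 10.4 shows that the authors could separate the qualitative parts from Aim 4 when they chose to. Section 3.1 falls short of the definition in the document's own footnote. The text provided nowhere joins a primary measure to a reporter and a time point, and with a sample this small a result in one reporter only is likely. On this view the remedy is cheap: limit 1.2, list outcomes in 3.1, and present Aim 4 as pilot estimation with intervals.

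The wording conflict stands, and so does the lack of detail. The rest is weaker. Footnote 2 is explanatory form text, and the completion events in 3.1 sit beside it as an omission, not a contrary claim. The instruments may be identified in the surveys that the protocol says are attached elsewhere, which were not available here. The split percentages answer a different question from the one about 1.2 and 3.1, and they assume each reporter is judged separately at 0.05, which 14.1 does not say.

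The remedy also carries costs. Estimates at every post-baseline time point would be an analysis that 14.1 does not state, with visit numbers that vary between families. Dropping the efficacy question would give up something the sponsor chose to power, and would leave 10.4 out of line unless it too were rewritten.

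**Conclusion.** The inconsistency is genuine, but it is one of wording and documentation. An analyst following 14.1 and the front-page note would fit the same model to the same outcomes, compare the same conditions and obtain the same estimates and intervals whether or not 1.2 and 3.1 were tidied. The effect on the results is therefore nil. What is left open (instrument, reporter, time point) is detail that the team can record when reporting. Whether a small pilot should be framed as a test or as estimation is a fair trade-off on which the plan has taken a position.

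The 18% to 32% figure does not alter this. It rests on an assumed correlation, on separate tests at 0.05 and on an effect of 1.06 SD, well above the 0.59 to 0.60 SD in 10.4. It reflects the sample size, not the wording of 1.2 or 3.1. This conclusion assumes that 14.1, as simplified by the front-page note, is the operative analysis. It does not cover the accuracy of the power statement in 10.4, which is a separate matter.
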